#### **4.2.2 Missing data**

With respect to AEs, events with missing intensity will be assumed to be severe. Events with missing relationship to LCM per the investigator will be assumed to be related.

To assess the change and percent change in seizure days for any generalized seizures from the Baseline Period to the Maintenance Period for subjects who prematurely discontinue the study, a

last observation carried forward convention will be applied in the following manner to obtain an estimate for the Maintenance Period:

- Subjects discontinued prematurely during the Titration Period: estimates will be calculated using all available data in the Titration Period and carried forward for the Maintenance Period.
- Subjects discontinued prematurely during the Maintenance Period: estimates will be calculated using all available data in the Maintenance Period and carried forward for the entire Maintenance Period.
- Subjects completing the Maintenance Period: estimates will be calculated using all data from the Maintenance Period.

Missing values for other safety or preliminary efficacy variables will be not imputed.

No imputation of missing values associated with an individual date or visit is planned, with the exception of partial date information for AEs and medications in order to determine whether they are treatment-emergent or concomitant, respectively, and for medical resources to define in which study period these were used. For details see Section 4.2.3.

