13.6 Handling of dropouts or missing data

Subjects who prematurely discontinue the study will be evaluated based on the data collected at each visit attended.

To assess the change and percent change in seizure days for generalized seizure types (absence, myoclonic, clonic, tonic, tonic-clonic, atonic, and partial evolving to secondarily generalized) and any generalized seizures from the Baseline Period to the Maintenance Period for subjects who prematurely discontinue the study, a last observation carried forward convention will be applied in the following manner to obtain an estimate for the Maintenance Period:

- Subjects discontinued prematurely during the Titration Period: estimates will be calculated using all available data in the Titration Period and carried forward for the Maintenance Period.
- Subjects discontinued prematurely during the Maintenance Period: estimates will be calculated using all available data in the Maintenance Period and carried forward for the entire Maintenance Period.
- Subjects completing the Maintenance Period: estimates will be calculated using all data from the Maintenance Period.

The imputation for data will not be carried forward into the End-of-Study Period.

No further substitution of missing data will be conducted.

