### **2.3 Study design and conduct**

SP0966 is a Phase 2, multicenter, open-label exploratory study designed to assess the safety and preliminary efficacy of oral LCM as adjunctive therapy for epilepsy syndromes associated with generalized seizures in pediatric subjects  $\geq 1$  month to  $< 18$  years of age.

The study treatment is LCM in either the oral solution formulation or tablet formulation. The formulation of LCM to be administered is based on the weight of the subject.

Subjects will not be randomized, but all subjects who sign the informed consent form at Visit 1 will be assigned a unique identification number.

Approximately 50 subjects will be enrolled at approximately 50 sites in Europe, and North America, and other regions as deemed necessary. It is planned to enroll approximately 40 subjects between 4 years and  $< 18$  years of age and at least 10 subjects between 1 month and  $< 4$  years of age.

The study will begin with subject screening at Visit 1 and will consist of a 6-week prospective Baseline Period. If all inclusion criteria are met and no exclusion criterion is met, the subject will begin a 6-week Titration Period (LCM dosing flexibility allowed based on tolerability) starting at Visit 2. Subjects will initiate treatment with LCM oral solution at 2mg/kg/day, or LCM tablets at 100mg/day based on body weight. The dose will be titrated to a level to optimize tolerability and seizure control, not to exceed 12mg/kg/day (oral solution) for subjects weighing  $< 50$ kg, or 600mg/day (tablets/oral solution) in subjects weighing  $\geq 50$ kg. Subjects will increase the LCM dose in a stepwise fashion on a weekly basis to optimize tolerability and seizure control.

At the end of the Titration Period (Visit 6), a 12-week Maintenance Period will begin. The LCM dose will remain stable throughout the Maintenance Period. Subjects who require a change in dose during the Maintenance Period will be withdrawn from the study.

The end of the Maintenance Period will be Visit 9, or, if subjects withdraw early, the ET Visit. Subjects may be eligible for participation in the additional open-label study (SP848). Subjects who choose not to participate in the open-label study or subjects who discontinue due to other reasons will enter a 2- to 4-week Taper Period followed by a Safety Follow-Up Visit 2 weeks ( $\pm 2$  days) after the final dose of LCM and a Safety Follow-Up Telephone Contact 30 days ( $\pm 1/+3$  days) after the final dose of LCM.

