### 3.2.3 Study periods

For the purpose of analyses, the following periods are defined.

- Baseline Period:

The Baseline Period is defined as the period of time from the date of Visit 1 to 1 day prior to the date of first dose of LCM. For the definition of Baseline values see Section 3.3.

- Titration Period:

The Titration Period is defined as the period of time from the date of first dose of LCM to the date of Visit 6 or the date of ET, whatever occurs first. If Visit 6 and ET are missing the Titration Period ends at the date of last dose of LCM.

- Maintenance Period:

The Maintenance Period is defined as the period of time from the day after the date of Visit 6 to the date of Visit 9/ET. If Visit 9/ET is missing the Maintenance Period ends at the date of last dose of LCM.

- Treatment Period:

The Treatment Period is defined as the combined Titration and Maintenance Period, ie, starts at the date of first dose of LCM and ends at Visit 9/ET. If Visit 9/ET is missing the Maintenance Period ends at the date of last dose of LCM.

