### 8.1.2 Generalized seizures

Days with any generalized seizures per 28 days (GSD/28d) will be based on the seizure diary and will be derived separately for the Baseline Period, the Titration Period, and the Maintenance Period. Basis for the calculation will be the number of days with at least 1 generalized seizure (GSD) (absence, myoclonic, clonic, tonic, tonic clonic, atonic, partial evolving to secondarily generalized) during the considered study period and the number of days in the considered study period for which seizure information was provided (D):

$$\text{GSD/28d} = \text{GSD} \times (28/\text{D})$$

The days with any generalized seizures per 28 days will only be derived for subjects who completed or discontinued during the respective study period. For subjects who discontinued during the Titration Period, the missing value of the Maintenance Period will be imputed as described in Section 4.2.

Descriptive statistics will be provided for actual values and changes from Baseline for days with any generalized seizures per 28 days by study period. This summary will be repeated by syndrome subgroups (as described in Section 4.8).

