## 9.2 Exploratory Efficacy Variables

The analysis of the exploratory efficacy variable will be conducted for the FAS.

Days with seizures per 28 days for each seizure type and study period will be calculated as described for the generalized seizures in Section 8.1.2. The days with any generalized seizures

per 28 days will only be derived for subjects who completed or discontinued during the respective study period. For subjects who discontinued during the Titration period, the missing value of the maintenance period will be implemented as described in Section 4.2

Descriptive statistics will be used to summarize the proportion of subjects who have at least a 50 percent reduction in generalized seizures per 28 days by study period (Titration and Maintenance Period) and syndrome subgroup.

Descriptive statistics will also be produced to summarize the proportion of subjects who have more than 30% and 50% increase in generalized seizures per 28 days during the study period (Titration and Maintenance Period) by syndrome subgroup.

Descriptive statistics will be produced to summarize the percent change in days with any generalized seizures per 28 days during the study period by syndrome subgroup.

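### The carried-forward Maintenance value has no minimum number of diary days, so an early withdrawal with few seizure days at Baseline is scored as a ≥50% responder, or as worsened, largely by chance

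*SAP*

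**What the plan says.** The rule is built from several sections.

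- SAP 4.2.2 covers withdrawal during Titration: "estimates will be calculated using all available data in the Titration Period and carried forward for the Maintenance Period". Protocol 13.6 has the same rule.
- For withdrawal during Maintenance, protocol 13.6 says "estimates will be calculated using all available data in the Maintenance Period and carried forward for the entire Maintenance Period", and SAP 4.2.2 agrees. The six weeks of Titration diary are not used.
- SAP 8.1.2 defines days with any generalized seizure per 28 days as GSD × (28/D), where D is the "number of days in the considered study period for which seizure information was provided". It sets no lower limit on D.
- SAP 3.2.3 lets the Titration Period run "from the date of first dose of LCM to the date of Visit 6 or the date of ET, whatever occurs first", so it can be short. SAP 3.5.2 admits a child to the Full Analysis Set on one post-Baseline efficacy assessment.
- SAP 9.2 connects the rule to the exploratory variables: "For subjects who discontinued during the Titration period, the missing value of the maintenance period will be implemented as described in Section 4.2". These include the proportion with "at least a 50 percent reduction in generalized seizures per 28 days by study period" and syndrome, and the proportions with increases above 30% and above 50%.

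No non-responder rule for discontinuations is stated, and no analysis without the carried-forward values is planned.

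**The concern.** The period being estimated is 12 weeks ("a 12-week Maintenance Period will begin", SAP 2.3), but the estimate may rest on two or three diary days. Take a child with 4 seizure days in the 42 Baseline days who leaves with 3 diary days and no seizure yet. The formula gives 0 × 28/3 = 0, so the child is tabulated as a 100% reduction in a Maintenance Period that was never entered. If one of the three days had a seizure, the same child would be tabulated as more than 50% worse.

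Early withdrawal is foreseen: protocol 6.3 requires it for intolerable adverse events, and protocol 7.2 withdraws children who cannot reach the minimum dose. A treatment failure on tolerability can therefore appear as an efficacy success. The tables affected are split by syndrome and shown for groups as small as 4 (SAP 4.8), where one child is 25 percentage points. The same rule feeds the second primary safety variable, the change in days with any generalized seizure.

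**Working it through.** The plan states no false-responder rate, dropout rate or sample size calculation, so there is no figure of its own to reproduce. The check applies the SAP's formula under no treatment effect.

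**Inputs**
- Baseline length: 42 days (6 weeks). B is the number of Baseline seizure days. Inclusion criterion 5 requires at least 2 events, so B can be 1 or 2 at the floor. No upper limit or expected value is given.
- D: diary days available after first dose.
- Full Maintenance Period: 84 days.

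**Assumptions**: each day is a seizure day with probability p = B/42, independently, at an unchanged rate. SAP 9.2 speaks of seizures per 28 days but derives seizure days, so days are used here.

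**Formulas**, with X ~ Binomial(D, p):
- P(≥50% responder) = P[X ≤ floor(0.5 × D × p)]
- P(>50% increase) = P[X > 1.5 × D × p]

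**Worked cases**
- B = 4, D = 3: 0.5 × 3 × 4/42 = 0.14, so only X = 0 qualifies, and (38/42)³ = 0.741.
- B = 12, D = 7: 0.5 × 7 × 12/42 = 1, so X ≤ 1 qualifies, giving 0.360.

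| B of 42 | per 28 days | Responder, D=3 | D=7 | D=14 | D=84 | >50% increase, D=3 |
|---|---|---|---|---|---|---|
| 1 | 0.67 | 93% | 85% | 71% | 40% | 7% |
| 2 | 1.33 | 86% | 71% | 51% | 23% | 14% |
| 4 | 2.67 | 74% | 50% | 25% | 9% | 26% |
| 6 | 4.0 | 63% | 34% | 39% | 3.5% | 37% |
| 12 | 8.0 | 36% | 36% | 19% | 0.2% | 20% |
| 21 | 14.0 | 12.5% | 6% | 3% | <0.1% | 12.5% |
| 42 | 28.0 | 0 | 0 | 0 | 0 | 0 |

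Whenever D < 84/B (42 days for B = 2, 21 for B = 4, 14 for B = 6, 7 for B = 12), one seizure day is enough to fail, so every responder is recorded at 100%. In the other direction, one seizure day in three diary days is 28/3 = 9.33 per 28 days. That is +600% for B = 2 and +250% for B = 4.

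**Uncertainty in the Baseline rate.** A beta-binomial version with a Jeffreys prior gives 84% / 68% at D = 3 / 7 for B = 2, 72% / 49% for B = 4 and 37% / 37% for B = 12. The short-diary figures hardly move. The 84-day comparators rise to 29%, 19% and 4%.

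**Primary variable.** At a constant rate the expectation of GSD × 28/D does not depend on D. Its standard deviation is 28 × √(p(1−p)/D). For B = 12 this is 28 × √(0.204/3) = 7.3 at D = 3, against 28 × √(0.204/84) = 1.4 over 84 days.

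**Illustrative cohort (assumed).** Suppose 5 of 50 children leave with 2 to 6 diary days, all at B = 6. Their mean chance of response is 55.3%, so the no-effect responder rate is (5 × 0.553 + 45 × 0.035)/50 = 8.7%, against 3.5% with none leaving. If 2, 5 or 8 children leave with 7 diary days, the expected chance responders among them are 1.4, 3.6 or 5.7 at B = 2; 1.0, 2.5 or 4.0 at B = 4; and 0.7, 1.8 or 2.9 at B = 12.

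**The case against.** Several points on the other side stand.

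- A reader might infer that children who leave in the first days are generally counted as responders. The documents do not support that. The chance depends on Baseline frequency, which they do not give. At 12 of 42 most such children would not be responders, and with daily seizures none would.
- A reader might also infer a one-way bias towards benefit. The same values feed the increase proportions, and children withdrawn for seizure worsening (protocol 6.3) would rarely score as responders. For the primary mean change the carried value adds noise. Medians are also planned (SAP 3.1), and Titration values are summarised separately (SAP 8.1.2).
- It is tempting to read the responder table as the go/no-go criterion. Protocol 5.4 describes exploratory work to find syndromes that benefit and to exclude those that do not. It names no responder threshold, and the variable is exploratory and descriptive.
- Stopping on Day 3 need not mean D = 3, because Titration runs to the Early Termination date and the diary continues. D can exceed the days on drug.
- Disposition with reasons is shown by period and by syndrome (SAP 5.1), and full listings are planned. A careful reader could trace the affected children. Also, 25 points per child is a property of any group of 4.

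These points limit the size and direction of the effect. They do not remove it: the current text assigns a Maintenance response status to children who never entered or hardly entered that period, and no planned table separates them.

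**Conclusion.** The point holds in a conditional form. Read literally, the plan turns any number of diary days into the Maintenance value. For children with low to moderate Baseline frequency, a withdrawal in the first week is then classified largely by chance: about 34% to 86% false ≥50% response for 2 to 12 Baseline seizure days, against 0.2% to 23% over a full 84 days. At three diary days, 14% to 37% of children with 2 to 6 Baseline seizure days would be falsely shown as more than 50% worse. At 21 of 42 the false-response chance is 12.5% / 6% at 3 / 7 diary days, and with daily seizures it is nil.

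The figures assume independent days, a constant rate and no drug effect. The effect on the trial as a whole cannot be fixed, because neither Baseline frequency nor early dropout is stated. The responder and increase tables by syndrome are the ones at risk. The second primary variable loses precision but is not pushed one way if the rate is constant. The change is worth making before database lock, but it does not undermine the study.

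**What to change.** - **SAP 9.2:** count a subject who discontinues before completing the Maintenance Period as a non-responder in the Maintenance ≥50% responder table. Leave the Titration table on observed Titration data. The responder proportion is defined only in the SAP, so this leaves the protocol 13.6 rule for change and percent change untouched.
- **SAP 4.2.2 and 8.1.2:** keep the carry-forward as the main display for the second primary variable. Add one summary of that variable, and of the increase proportions, without subjects whose carried-forward value rests on few diary days (for example fewer than 14). Flag those subjects in the listing.

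A minimum-days rule that drops subjects is not recommended. At 14 days the chance of false response is still 51%, 25%, 39% and 19% for 2, 4, 6 and 12 Baseline days, and the rule would remove early withdrawals, including any who worsened, from a primary safety variable.

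The cost is a sentence or two of SAP text, one extra summary, and a slightly less favourable Maintenance responder proportion.

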#### **4.2.3 Incomplete or missing dates for adverse events and concomitant medication**

For analyses of AEs and concomitant medication usage, a complete date must be established in order to correctly identify the AE or medication as occurring during treatment in the study or not. For the purposes of imputing missing components of partially-reported start and stop dates for AEs and for medication use, the algorithms listed below will be followed. Start and stop dates of AEs or concomitant medication will be displayed as reported in the subject data listings (ie, no imputed values will be displayed in data listings).

- Missing start day, but month and year present:

If the start of LCM occurred in the same month and year as the occurrence of the AE/concomitant medication, the start day of the event/concomitant medication will be assigned to the day of first administration of LCM.

Otherwise the start day will be set to the 1st day of the month.

- Missing start day and month, but year present:

If the start of LCM occurred in the same year as the occurrence of the AE/concomitant medication, the start day and month will be assigned to the date of first administration of LCM.

Otherwise the start day and month will be set to January 1st.

- Missing end day, but month and year present:

The end day will be set to the last day of the month.

- Missing end day and month, but year present:

The end day and month will be set to the date of study termination or the date equivalent to 30 days after last dose of LCM, whatever occurs later.

However, if the study termination year and year for the date which is 30 days after the last Dose of LCM are greater than the event/concomitant medication year, the day and month are to be set to December 31st.

An AE with a completely missing start date will be considered treatment-emergent if the end date of the AE is not on or before the date of first dose of LCM.

With respect to the definition of medication as concomitant, the following rule will be applied in case of completely missing stop and/or start date information:

Medications with a missing stop date and a start date prior to the date of last administration of LCM will be considered as concomitant medication. Medications with a missing start date whose stop date is either unknown or after the date of the first application of LCM will be considered as concomitant medication, but not as prior medication. Medications with missing start date whose stop date is prior to first administration of LCM will be considered as prior medication, but not as concomitant medication.

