### **6.4 Prior and concomitant medications**

Medications will be considered as prior if the start date of the medication is before the date of first dose of LCM. Medications will be considered as concomitant if it was taken at least once during treatment with LCM (ie, from the date of first administration of LCM through the date of last administration of LCM). Medications starting prior to first dose of LCM and continuing during treatment with LCM will be considered both, prior and concomitant medication.

For cases of partial or missing dates the rules described in Section 4.2.3 will be applied.

The number and percentage of subjects taking concomitant AEDs will be summarized by WHO-DD chemical subgroup (Level 4) and preferred drug name for the SS.

The number and percentage of subjects taking prior and concomitant medications (excluding AEDs) will be summarized separately by WHO-DD anatomical main group (Level 1) and therapeutic subgroup (Level 2) for the SS.

Vagus nerve stimulation will only be listed.

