### 8.2.2 Adverse events

Treatment-emergent AEs (TEAE) are defined as those events which start on or after the date of first LCM administration and within 30 days following the date of last LCM administration, or whose severity worsens within this time frame.

Other significant AEs are defined in Appendix 13.1 (Table 13-1).

An overall summary of AEs will provide the numbers and percentages of subjects with at least 1 TEAE, serious TEAE, other significant TEAE, TEAE that led to discontinuation, drug-related TEAE, drug-related serious TEAE, severe TEAE, AE leading to death, and TEAE leading to death. The AE overall summary will be repeated by syndrome subgroups (as described in Section 4.8).

The following summaries of AEs will be provided by primary SOC and PT:

- TEAEs
- TEAEs during the Titration Period
- TEAEs during the Maintenance Period
- TEAEs by syndrome subgroups (as described in Section 4.8)
- TEAEs including subject numbers

- Serious TEAEs
- Serious TEAEs including subject numbers
- TEAEs leading to discontinuation
- TEAEs leading to discontinuation including subject numbers
- TEAEs by maximum intensity
- Nonserious TEAEs
- Nonserious TEAEs occurring in > 5% of subjects
- Other significant TEAEs

The following summaries by primary SOC and PT will be presented overall only (ie, not by age group).

- TEAEs by relationship to LCM
- Serious TEAEs by relationship to LCM
- Nonserious TEAEs by relationship to LCM
- Fatal TEAEs by relationship to LCM
- Nonserious TEAEs occurring in at least 5% of subjects by relationship

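### The partial-date rule in SAP 4.2.3 ignores a known end date, so an AE that ended before the first LCM dose can be counted as treatment-emergent and a medication can lose its prior status

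*SAP*

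**What the plan says.** SAP 4.2.3 completes partial start dates so that each AE or medication can be placed inside or outside the treatment period. Two branches matter:

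- Start day missing, month and year equal to those of the first LCM dose: "the start day of the event/concomitant medication will be assigned to the day of first administration of LCM".
- Start day and month missing, year equal to that of the first dose: "the start day and month will be assigned to the date of first administration of LCM".

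In all other cases the start becomes the 1st of the month or 1 January. Neither branch refers to the end date.

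The section does use the end date when the start is completely missing. For AEs: "An AE with a completely missing start date will be considered treatment-emergent if the end date of the AE is not on or before" the first-dose date. For medications, "the following rule will be applied in case of completely missing stop and/or start date information", and it includes: "Medications with missing start date whose stop date is prior to first administration of LCM will be considered as prior medication".

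The definitions that use these dates are as follows. SAP 8.2.2 defines TEAEs as "those events which start on or after the date of first LCM administration and within 30 days" after the last dose, or as events that worsen in that window. In SAP 6.4, "Medications will be considered as prior if the start date of the medication is before the date of first dose of LCM", and "Medications will be considered as concomitant if it was taken at least once during treatment with LCM". SAP 6.4 refers partial medication dates to 4.2.3, and SAP 9.1.5 uses 4.2.3 to assign health care resource use to study periods.

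**The concern.** The purpose of the imputation is to decide whether a record belongs to the treatment period. If the end date precedes the first dose, that question is already answered, and the imputation overrides the answer. The result is also perverse: a record with a known start month or year is classified worse than one with no start date at all.

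Elsewhere the SAP keeps imputed dates within known facts. SAP 4.2.4 caps an imputed last dose at the date of death. SAP 6.2 does not let an imputed diagnosis date precede the birth date or, where available, the first seizure. The missing check in 4.2.3 looks like an oversight.

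AEs are a secondary safety variable, and Protocol 11.1.1 collects them from consent, so pre-treatment AEs will be in the database. A misplaced event would enter the TEAE tables and, by its imputed start, the Titration Period table. Cells are small: about 50 subjects in total, at least 10 under 4 years, and syndrome subgroups shown from 4 subjects upwards.

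**Working it through.** The plan states no figure on this point, so the check applies its rules literally to test records.

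**Inputs**
- Start and end imputation: SAP 4.2.3 (a missing end day becomes the last day of the month).
- TEAE test, SAP 8.2.2: F ≤ start ≤ L + 30 days, where F is the first and L the last LCM dose date.
- Prior test, SAP 6.4: start < F. Concomitant test, read as overlap: start ≤ L and stop ≥ F.
- Assumed for illustration: F = 20 March 2015 and L = F + 125 days = 23 July 2015, so L + 30 = 22 August 2015.

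**Results under the SAP as written**

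| Reported start | Reported end | Imputed start | End used | End minus start | TEAE |
|---|---|---|---|---|---|
| March 2015 | 10 March 2015 | 20 March | 10 March | −10 days | yes |
| 2015 | 10 March 2015 | 20 March | 10 March | −10 days | yes |
| 2015 | February 2015 | 20 March | 28 February | −20 days | yes |
| March 2015 | 25 March 2015 | 20 March | 25 March | 5 days | yes |
| March 2015 | March 2015 | 20 March | 31 March | 11 days | yes |
| February 2015 | 10 March 2015 | 1 February | 10 March | 37 days | no |
| missing | 10 March 2015 | none | 10 March | none | no |

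The first three rows are wrong: each event was over before 20 March. Rows four and five are ambiguous, and the default to first dose is reasonable there. The last row is the first record with less information, and it is classified correctly.

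**Medications.** With the dates of the first three rows, the imputed start (20 March) is not before F, so the medication is not prior. The stop is before F, so it is not concomitant. It falls in neither class. With a completely missing start, SAP 4.2.3 would make it prior.

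**Size of the exposed window** (assuming a 42-day Baseline and first doses spread evenly over the calendar, 2013 to 2016)
- Same month: a first dose on day d of a month has d − 1 earlier days in that month. Over the 1,461 dates these sum to 21,520, and 21,520/1,461 = 14.7 days; 14.7/42 = 35% of Baseline.
- Same year: only first doses on days 1 to 42 of a year lose Baseline days to the previous year, in total 42 × 43/2 = 903 per year. 42 − 903/365.25 = 39.5 days; 39.5/42 = 94% of Baseline.

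These are shares of Baseline days on which the rule could act, not rates of affected records.

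**Effect of one misclassified subject on one table row** (if that subject has no other event in the row): 1/50 = 2 percentage points overall, 1/10 = 10 in an age group of 10, 1/4 = 25 in a syndrome subgroup of 4.

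**The case against.** Four arguments can be made for leaving the text alone.

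- **Few or no records may be affected.** The fault needs a partial start and an end before first dose on the same record. Baseline AEs are collected prospectively at Visit 1, the Week -3 call and Visit 2, and Protocol 12.3.2 provides computerized and manual discrepancy checks. The documents give no partial-date rate. This stands: such records may occur, and the number could be zero.
- **The default is conservative.** It matches SAP 4.2.2, where missing intensity is taken as severe and missing relationship as related, and a single-arm descriptive study has no between-arm comparison to distort. This holds for ambiguous records. It does not justify the default where the end date excludes treatment emergence.
- **No impossible date is reported.** A reader might infer from the table above that AEs with negative duration will be reported. The documents do not support that. SAP 4.2.2 restricts date imputation to classification and period assignment, 4.2.3 keeps imputed dates out of the listings, and 8.2.2 plans no AE-duration summary. The negative differences only show that the imputed interval contradicts the record.
- **The medication effect is minor.** This stands. A reader might infer that such a medication becomes concomitant, but SAP 6.4 requires actual use during LCM treatment. The loss is an entry in the descriptive prior-medication table.

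**Conclusion.** The rule is wrong as written for a narrow, identifiable class of records: a partial start matching the month and year, or the year alone, of first dose, and an end date before first dose. Within that class every AE that meets the rule is misclassified as a TEAE and every such medication drops out of the prior class. No other section of the SAP corrects this.

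The practical size is unknown and probably small. A reader might also infer that a year-only start exposes any AE that ended earlier in that year. It does not: AE collection starts at consent, so exposed events lie in the Baseline Period of about 6 weeks. In the example that runs from about 6 February (20 March minus 42 days) to 19 March.

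The conclusion rests on the SAP text alone. The example dates and the even-calendar assumption affect only the illustrations.

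**What to change.** Amend SAP 4.2.3 as follows:

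- Apply the first-dose imputation only if the end or stop date is missing or, after any imputation of a partial end date, falls after the first LCM dose date.
- Otherwise impute the start as the 1st of the month (start day missing) or 1 January (day and month missing).
- Classify such an AE as pre-treatment. This uses the same on-or-before boundary as the rule for AEs with a completely missing start.
- Classify such a medication as prior, and as not concomitant if it stopped before the first dose.

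State the AE class explicitly and do not leave it to the imputed date. If the first dose is itself on the 1st of the month and the AE ended that day, the imputed start equals the first-dose date and SAP 8.2.2 would still count a TEAE.

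Carry the same condition to SAP 9.1.5, so that health care use that ended before treatment is not counted in Titration. Because 1 January can fall before Visit 1, and so outside the Baseline Period of SAP 3.2.3, say there that such records count in Baseline unless they are known to precede Visit 1.

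In the example, the first three rows then become pre-treatment, and rows four and five stay TEAEs with a start of 20 March. The cost is a few lines of SAP text and one programming condition, with no change to data collection.
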